1.4 Study Rationale

Unfortunately, 25% of CAH and 37% of EC patients go on to relapse after treatment with hormonal therapy. Relapse of CAH/EC patients after treatment with progesterone is thought to be related to progesterone resistance. Metformin is a generic oral anti-hyperglycemic. Recent evidence suggests that metformin reduces cancer risk and cancer deaths among diabetic patients (17-19). Based on preclinical *in vitro* and *in vivo* studies, metformin demonstrates anti-proliferative effects for both endometrial hyperplasia and cancer through inhibition of the mTOR pathway. Metformin has also demonstrated reversal of progesterone-resistance in endometrial cancer cell lines. In clinical data, metformin has been associated with decreased cellular proliferation (via Ki-67 staining) in endometrial cancer specimens of patients undergoing primary surgical management. Given our promising preclinical data, we hypothesize that the addition of metformin to standard LR-IUD progestin therapy will result in a CR rate at 6 months that is significantly higher than 50%. The comparator rate of 50% is based on results reported in the meta-analysis referenced earlier, and because a response rate significantly greater than this will be considered clinically meaningful by the investigators. The rate of CR at 6 months is our primary interest as this was the median time to response in the meta-analysis (12). Due to metformin's long term and wide spread use in patients with significant comorbidity, as well as proven safety and efficacy in healthy women with PCOS and non-diabetics, it is an ideal medication to evaluate in a population of non-surgical candidates.

In addition, our proposed clinical trial of metformin in combination with the LR-IUD will complement the proposed GOG trial in that we will (1) explore the potential activity of metformin in CAH and early stage EC patients as opposed to the advanced and recurrent patient population, and (2) we will investigate the combination of metformin with hormonal as opposed to cytotoxic therapy. If these study results are positive, we plan to propose a multicenter GOG trial of this treatment regimen, to establish a new standard of care for non-surgical patients with CAH/EC.

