3.1.7 Understand study design, risks, and benefits and have signed informed consent

3.2 Exclusion Criteria

Any patient meeting any of the exclusion criteria at baseline will be excluded from study participation.

3.2.1 Evidence of renal dysfunction ($\text{Cr} > 1.5\text{mg/dL}$ or Cr clearance $< 60\text{mL/m}^2$) or liver dysfunction ($\text{AST/ALT} > 2\text{x upper limit of normal (ULN)}$)

3.2.2 Current use of progestin therapy (local, topical, or systemic) that has been ongoing for > 3 months

3.2.3 Myometrial invasion $>50\%$ or evidence of nodal or metastatic disease on baseline MRI (MRI only to be done for EC patients)

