4.2 Dilation and Curettage (D&C)

As part of standard of care in treating CAH and EC with non-surgical progestin therapy, patients will undergo a D&C procedure for definitive diagnosis and therapeutic effect. During this procedure, the LR-IUD is placed. D&C is a safe, outpatient procedure that will be performed by a gynecologic oncology attending, fellow, or resident. In this procedure, the uterine lining tissue is removed with standard curette instruments. The main risk of this procedure is uterine perforation, which occurs at a rate of 1-2%. D&C would be performed regardless of study enrollment, and is not considered part of the current study. However, confirmation of CAH or EC will not be made, and therefore metformin will not be started, until after results of the D&C are read by the PI. This will occur within 3 days of receipt of the results and 7 days of the procedure and the patient will be informed that they can then initiate metformin. If a patient's provider does not feel

that they require a D&C procedure, the LR-IUD may be placed in clinic. The patient will undergo screening and pre-treatment testing at this time or the visit prior to the LR-IUD placement and will start the metformin within 30 days of IUD placement. Note that screening must occur within 30 days of starting treatment.

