6.0 EVALUATIONS AND ASSESSMENTS

6.1 Time and Events Table

	Screening	Pre-treatment Visit	Month (Mo) 1 Week (Wk) 1	Mo3	Mo6	Mo9	Mo12	Early Termination ²	Final Study Encounter ²
Inclusion/ Exclusion Criteria	X								
History ¹ and Physical	X			X	X	X	X		
Informed Consent	X								
Education of potential side effects		X							
Pregnancy test (serum), if applicable	X ³								
Random (non-fasting) glucose		X						X	
AST/ALT	X				X	X	X	X	
Serum creatinine	X				X	X	X	X	
Cervical cultures ⁴	X								
MRI or Pelvic US ⁵	X								
D&C, LR-IUD insertion		X							
Pregnancy test (urine)	X ³								
Metformin Treatment ⁶									
AE Assessment									
Patient Diary			X			X ⁷		X	
Request tissue	X ⁸								
Endometrial Biopsy				X	X ⁹	X	X		
Blood and urine collection ¹⁰	X			X	X	X	X	X	

Metformin treatment begins D1 of Month 1; continue as per sections 4.3-4.4

Footnotes to Time and Events Table

¹Comprehensive medical history at baseline; thereafter history focused on symptoms and toxicities

²Patients will be followed until final study encounter, which will occur within 30 days of their final endometrial biopsy while on metformin. Metformin is to be stopped the day of the 12-month endometrial biopsy, or the day on which the results of prior biopsies are known, if they indicate disease progression. In the case of ongoing adverse events/serious adverse event, patients will be followed to resolution of the event. If early termination of the study occurs (i.e., prior to 12 months), the patient will be asked to have serum and urine collected, and the patient followed-up until any treatment related adverse events have resolved or returned to baseline. Their standard of care every 3 month (+/- 2 weeks) endometrial biopsy will be performed as scheduled by their physician as per routine care.

³Women of childbearing potential (WOCBP) must have negative urine pregnancy test within 7 days of D1 of treatment; urine pregnancy test (for WOCBP) will be conducted on the day of outpatient surgery as well, per standard of perioperative care.

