6.2 Screening

Women with CAH/grade 1 endometrial cancer will be recruited from the Gynecologic Oncology and Gynecology clinics at participating centers. All patients will already have had a baseline endometrial biopsy performed, to establish their diagnosis and referral to the gynecologic oncology clinic. A sample of this tissue will be requested from the referring physician. All patients will have a urine pregnancy test (if of childbearing age), gonorrhea and chlamydia cervical cultures if they are age 24 or younger, and baseline serum creatinine, glucose and liver enzymes drawn at the time of their screening visit. These labs will be reviewed by the principal investigator. Note that screening labs must occur within 30 days of starting treatment.

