6.3 Pre-Treatment

Per standard course of treatment, all women undergoing IUD placement for the treatment of CAH/EC will undergo dilation and curettage (D&C) procedure to confirm histologic diagnosis and for placement of the IUD if deemed necessary by their primary provider. Urine pregnancy test (for women of childbearing age) will be conducted on the day of outpatient surgery as well, per standard of perioperative care at UNC. Final pathology results from the D&C will be reviewed by the principal investigator. The patient will be notified within 3 days of the receipt of results, confirming CAH/grade 1 EC histology, that she is cleared to start study treatment with metformin. This will occur within 30 days of LR-IUD placement. Blood and urine samples will also be collected for correlative studies (see section 6.7). If the patient does not require a D&C, she will have a urine pregnancy test prior to IUD placement as is the standard of care and will start metformin within 30 days of IUD placement.

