8.2 Sample Size, Stopping Rule, and Accrual

The goal accrual is 32 patients (16 CAH, 16 EC) and we expect to enroll 1-2 patients/per month. Our power calculation and analysis will be based on 30 patients, assuming early discontinuation of 2 participants prior to 3 months of treatment. We estimate 18 months to complete accrual.

The primary objective of this study is to compare the CR rate at 6 months to a rate of 50% (the 50% is based on results reported in the meta-analysis referenced earlier, and because a response rate significantly greater than this will be considered clinically meaningful by the investigators). With a combined sample size of 30 evaluable patients with either CAH or grade 1 EC, and assuming a null CR rate of 50% and an alternative of 75%, we will have 80% power to conclude that the CR rate at 6 months is significantly higher than 50% using an exact test for a single proportion with a two-sided α of 0.05. Furthermore, the exact 95% confidence interval for the CR rate at 6 months will have a maximum width of 0.374. This means that the CR rate will be estimated within at least 18.7%. CAH and grade 1 EC represent a spectrum of neoplasia, which is why the two groups are being combined for the primary objective. The CR rate at 6 months will be estimated separately in the CAH and EC groups as a secondary objective.

Sequential boundaries will be used to suspend the trial if excessive toxicity is seen that requires discontinuation of metformin. If the study reaches a stopping boundary, it may be terminated by the PI, or submitted to the DSMC with a description of the toxicities and a rationale for why the study should be continued. At the patient level, metformin will be discontinued if a patient experiences: (1) a single grade 3 or higher metformin-related GI disturbance or grade 4 or higher hypoglycemic episode, or (2) two or more grade 2 side effects considered related to metformin therapy, or (3) if the patient requires a dose less than 850mg once daily. The accrual will be halted if the number of patients discontinuing metformin for one of the reasons above is equal to or exceeds b_n out of n patients who have been followed for toxicity for 3 months. This is a Pocock type stopping

boundary that assumes that a metformin discontinuation rate of 0.25 is acceptable, but anything $>25\%$ is unacceptable. If the true toxicity rate is equal to 0.25, the probability of crossing the boundary is 0.05.

Stopping Rule

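### When the D&C is omitted, a complete response reached on earlier progestin, before metformin starts, can be counted as a month-6 response

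*Combined protocol and SAP*

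**What the plan says.** **The null.** Section 8.2 tests the month-6 CR rate against 50% and explains that "the 50% is based on results reported in the meta-analysis referenced earlier". It adds that the investigators would regard a rate significantly above 50% as clinically meaningful. Section 1.2 gives the source rates, 66% for CAH and 48% for EC, without a time point. Six months enters separately, as the median time to response (1.2 and 1.4).

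**The clock.** Section 2.4.1 counts 6 months of treatment without naming the start. The table in 6.1 supplies it: "Metformin treatment begins D1 of Month 1".

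**Progestin before metformin.** Section 3.2.2 excludes "Current use of progestin therapy (local, topical, or systemic) that has been ongoing for > 3 months", so shorter current use is admitted. Before Amendment 8 (version dated May 15, 2020), any current use was excluded. On the path without a D&C, section 4.2 says the patient "will start the metformin within 30 days of IUD placement". Section 6.3 also gives 30 days, whereas the schema in 4.1 still gives 1 week.

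**Histology before metformin.** Section 6.2 states: "All patients will already have had a baseline endometrial biopsy performed, to establish their diagnosis and referral to the gynecologic oncology clinic". No maximum age is set for that biopsy, although the screening labs and the MRI for EC each have a 30-day limit. If a D&C is done, 4.2 and 6.3 hold metformin until its result has been read. The D&C is optional, however: where the provider does not feel "that they require a D&C procedure, the LR-IUD may be placed in clinic". For that woman 6.3 asks only for a pregnancy test: "If the patient does not require a D&C, she will have a urine pregnancy test prior to IUD placement". The first scheduled on-study biopsy is at month 3. Section 4.3 still reads as if every diagnosis were confirmed by D&C.

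**Analysis.** Section 8.3 has no summary, exclusion or sensitivity analysis by earlier progestin or by the last histology before metformin.

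**The concern.** Taken together, these provisions leave one route open. A woman is diagnosed on biopsy, starts progestin, is enrolled within 3 months, has the LR-IUD fitted in clinic without a D&C, and starts metformin. Her disease may already have gone. Nothing in the plan would show this before metformin, and a clear month-6 biopsy would count her as a responder.

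The hypothesis in 8.1 is that metformin plus LR-IUD produces a CR rate above 50%. A CR reached on earlier progestin was not produced by that regimen, whether 50% is read as a historical rate or as a chosen clinical threshold. Section 1.4 says a positive result would lead to a proposal for a multicenter trial.

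The route is not far-fetched. The Amendment 3 summary says that many women are diagnosed on biopsy alone and forgo the D&C, and that the design was changed to reflect this. Because Amendment 8 widened entry during the trial, earlier and later enrolees may also differ in progestin exposure within one pooled rate.

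**Working it through.** **1. The plan's own figure.** Inputs from 8.2: n = 30, null 0.50, alternative 0.75, exact test, two-sided alpha 0.05.
- P(X ≥ 20 | 0.50) = 0.0494, above 0.025. P(X ≥ 21 | 0.50) = 0.0214, below it. The cut-off is therefore 21 of 30.
- Power: P(X ≥ 21 | 0.75) = 0.803, which reproduces the stated 80%.

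**2. Longest progestin exposure.** 3 months (3.2.2) + about 1 month (30-day gap) = about 4 months at the first metformin dose. Adding 6 gives about 10 months at the month-6 biopsy, before the ±2-week window.

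**3. Two models with no metformin effect.** Both assume 50% CR at 6 months of progestin, a constant rate of clearing and no relapse. None of these is given in the documents.
- Model A, no ceiling: CR(t) = 1 − 0.5^(t/6). CR(4) = 0.370; CR(10) = 0.685.
- Model B, ceiling 0.57, an equal mix of the source rates (0.5 × 0.66 + 0.5 × 0.48): CR(t) = 0.57 × (1 − e^(−λt)), with λ = −ln(1 − 0.50/0.57)/6 = 0.350. CR(4) = 0.429; CR(10) = 0.553.

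**4. Effect on the test.** Suppose m women are at 10 months of progestin at the month-6 biopsy and the other 30 − m respond at 50%. X is the sum of the two binomial counts.

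| m | P(X ≥ 21), model B | P(X ≥ 21), model A |
|---|---|---|
| 0 | 0.0214 | 0.0214 |
| 3 | 0.0245 | 0.0332 |
| 5 | 0.0267 | 0.0440 |
| 10 | 0.0331 | 0.0847 |

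With m = 5, the expected number already in CR at the first metformin dose is 5 × 0.370 = 1.9 (A) to 5 × 0.429 = 2.1 (B).

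**5. The other reading of the source.** Suppose 57% is the eventual CR rate and 6 months is the median among responders only. Then CR(t) = 0.57 × (1 − 0.5^(t/6)), which is 0.285 at 6 months and 0.390 at 10. Even with all 30 women at 10 months, P(X ≥ 21 | 0.390) = 0.0006.

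**6. Size of a reduced sensitivity set.** The same exact two-sided test, if it were applied:
- n = 28: cut-off 20, power at a true 75% = 0.750.
- n = 25: cut-off 18, power = 0.727.

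**The case against.** The strongest reply is that the gap is narrow. It needs earlier progestin, an omitted D&C and early clearance in the same woman, and it could not arise from 3-month progestin use before Amendment 8. That stands, and it limits the size of the point. The data are also largely within reach: applying 3.2.2 requires the duration of progestin use, a comprehensive history is taken at baseline, and referral slides and blocks are requested. What is missing is their planned use in the analysis.

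Four stronger readings are tempting, and the documents do not support them.

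- *The null is a 6-month progestin rate, so a longer exposure makes it too low.* The documents never call 50% a 6-month rate. The source rates carry no time point, and step 5 shows a reading on which 50% is conservative.
- *Disease is never re-confirmed.* This is true only without a D&C. With one, histology is read before metformin, and re-confirmation after progestin would remove early responders, which pulls the other way.
- *The 30-day LR-IUD lead is itself a bias.* The LR-IUD is part of the tested regimen, so a CR after its placement arises within that regimen. The lead matters only for defining the clock.
- *One woman already in CR takes the error past 2.5%.* Fixing one certain CR and holding the other 29 at 50% gives P(Bin(29, 0.5) ≥ 20) = 3.1%. But extending that logic to several entrants holds those not yet in CR at 50%. Under model B they reach CR by month 10 in only (0.553 − 0.429)/(1 − 0.429) = 22%. That is why three entrants give 2.4% under that model.

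**Conclusion.** The point holds for women with earlier progestin who have no D&C. Following the plan as written, a CR that predates metformin can be counted as a month-6 response, and no planned analysis would separate it. The design calculation itself is correct.

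The size is modest and uncertain. Five entrants at the longest exposure move the chance of a positive result with no metformin effect from 2.1% to between 2.7% and 4.4%. This rests on an assumed number of entrants, maximum exposure in each, 50% CR at 6 months of progestin, constant hazard and no relapse. On the responder-median reading the test stays conservative. The direction of any error in the 50% null therefore cannot be settled from the documents, and no claim is made that the null is too low or that the test is anticonservative overall. What is at stake is how a positive result may be interpreted, and a small change protects that.

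**What to change.** Keep the primary exact test, alpha and N unchanged.

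1. State in 2.4.1 and 8.3 that month 6 counts from the first metformin dose.
2. Record the date progestin began, and the date and result of the last histology before metformin.
3. Pre-specify in 8.3 one sensitivity estimate: the 6-month CR rate with an exact 95% CI, excluding women who had progestin before the study LR-IUD and whose last CAH/EC-positive histology predates the start of that progestin.
4. Reconcile 4.1 (1 week) with 4.2 and 6.3 (30 days) on the interval from LR-IUD to metformin, and 4.3 (diagnosis confirmed by D&C) with 4.2 and 6.3 (D&C optional).

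The cost is two dates and one result per woman, mostly available from the history and the referral pathology, and one repeat of an estimate already planned. No visit, procedure or patient is added. The downside is a smaller set: power would be about 75% at n = 28 and 73% at n = 25 if it were tested, so it should be reported as an estimate only.

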4.4 Toxicities and Dosing Delays/Dose Modifications

Any patient who receives treatment on this protocol will be evaluable for toxicity. Each patient will be assessed weekly for the first 2 weeks, then every 30 days thereafter for the development of any toxicity according to the Time and Events table (6.0). Toxicity will be assessed according to the NCI CTCAEv4. Dose adjustments should be made according to the system showing the greatest degree of toxicity.

We anticipate that metformin related hypoglycemia and GI disturbances will be the two most common side effects. Metformin will be discontinued if the patient experiences (1) a single grade 3 or higher metformin-related GI disturbance or grade 4 or higher hypoglycemic episode, or (2) two or more grade 2 side effects considered related to metformin therapy, or (3) if the patient requires a dose less than 850mg once daily. Patients may request to stop the drug at any time.

See section 8.2 for a stopping rule related to the proportion of patients who must discontinue metformin due to toxicities for the study to be suspended.

Metformin Toxicity Dose Reductions	
Event	Action
Hypoglycemia	
Grade 1-2	Patient education, avoidance of fasting states
Grade 3	Decrease to metformin 850mg once daily
Grade 4	Discontinue metformin, follow-up per protocol

GI Distress	
Grade 1-2	Patient education, avoidance of fasting states
Grade 3	Discontinue metformin, follow-up per protocol

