4.7 Duration of Metformin Therapy

The planned duration of metformin therapy is 12 months. Metformin treatment will be discontinued early in the following scenarios:

- Progression of disease, as defined by CAH progression to invasive adenocarcinoma or grade 1 EC progression to grade 2 or 3 EC, at any of the standard of care biopsies at 3, 6, and 9 months. In any of these cases, metformin will be discontinued within 3 days of results of the biopsy.
- Unacceptable toxicity as defined by a single grade 3 or higher GI disturbance attributed to metformin, a single grade 4 or higher hypoglycemia episode, 2 or more grade 2 toxicities attributed to metformin, or requirement for a dose below 850 mg once daily.

Response to therapy will be assessed at 3-month intervals. As per standard of care, endometrial biopsies will be performed every 3 months (+/- 2 weeks) to assess histology and grade to determine response. This will be the basis of whether therapy should continue. If the 3 month biopsy demonstrates disease progression, the patient will be removed from protocol directed treatment and followed-up per protocol, and treatment decisions will be at the discretion of the treating physician. Otherwise, therapy will continue through 6 months. If the 6-month or 9-month biopsy demonstrates complete response (complete disease regression) or partial response (partial disease regression), metformin will be continued until 12 months of total therapy is given. If the 6-month or 9-month biopsy demonstrates stable disease, continuation of metformin on study will be at the discretion of the treating physician. Please see the schema (section 4.1) for clarity.

In addition, treatment will be stopped in the setting of:

- Inter-current illness that prevents further administration of treatment
- Pregnancy
- Patient decides to withdraw from study treatment, **OR**
- General or specific changes in the patient's condition render the patient unacceptable for further treatment in the judgment of the investigator.

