5.1.6 Adverse Events Associated with Metformin

The potential risks involved in metformin treatment are minimal but include gastrointestinal side effects, lactic acidosis, hepatotoxicity and hypoglycemia. All patients will have a serum pregnancy test (if of childbearing age) and baseline creatinine and liver enzymes drawn at the time of their enrollment. These labs will be reviewed by the principal investigator, and the patient notified that she has been cleared to take metformin per the inclusion/exclusion criteria. Patients will be contacted weekly during the first 2 weeks of metformin treatment and then every 30 days by the study coordinator to ensure that these women are not experiencing any appreciable side effects.

Hypoglycemia is a rare side effect of metformin in both diabetic and non-diabetic patients. See section 4.4.1 for information on management of hypoglycemia.

Please refer to the agent's package insert for a comprehensive list of adverse events.

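### The toxicity boundary in section 8.2 counts only three listed reasons for stopping metformin, so it can understate toxicity-driven discontinuation

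*Combined protocol and SAP*

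**What the plan says.** Section 8.2 states the purpose broadly: "Sequential boundaries will be used to suspend the trial if excessive toxicity is seen that requires discontinuation of metformin". Section 4.4 points to the same rule and describes it as concerning the proportion of patients forced off metformin by toxicity in general.

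The operative sentence in 8.2 is narrower: "The accrual will be halted if the number of patients discontinuing metformin for one of the reasons above is equal to or exceeds b_n". The reasons it refers to are:

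1. "a single grade 3 or higher metformin-related GI disturbance or grade 4 or higher hypoglycemic episode";
2. "two or more grade 2 side effects considered related to metformin therapy";
3. "if the patient requires a dose less than 850mg once daily".

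The denominator n is the number of patients with three months of toxicity follow-up. A rate of 0.25 is called acceptable, and the stated probability of crossing at that rate is 0.05. Section 8.2 calls the monitored quantity a discontinuation rate in one sentence and a toxicity rate in the next.

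Other routes off metformin appear elsewhere. Section 4.7 includes "General or specific changes in the patient's condition render the patient unacceptable for further treatment in the judgment of the investigator" and, separately, the patient's own decision to withdraw from treatment. Section 4.4 adds: "Patients may request to stop the drug at any time". Neither route is among the three reasons. Section 5.1.6 describes the drug's risks as follows: "The potential risks involved in metformin treatment are minimal but include gastrointestinal side effects, lactic acidosis, hepatotoxicity and hypoglycemia".

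**The concern.** The stated purpose and the counting rule agree only if the three reasons cover every toxicity-driven stop, and they do not. A stop for a single related event of grade 3 or higher, outside the gastrointestinal and hypoglycemic categories, would be made under the investigator-judgment clause of 4.7 and would add nothing to the count. A pair of related grade 2 events in any organ system would add one. The count is thus not ordered by severity. A woman who asks to stop because of a related side effect, without meeting one of the three reasons, is also left out.

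What is at stake is the sensitivity of the plan's only numerical halting rule. If the counted rate lies below the true rate of toxicity-driven stops, the boundary responds to the lower figure.

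**Working it through.** **Inputs (section 8.2).** Boundary b_n: none for n = 1 to 3; then 4, 5, 5, 5, 6, 6, 7, 7, 7, 8, 8, 9, 9, 9, 10, 10, 10 for n = 4 to 20; then 11, 11, 11, 12, 12, 12, 13, 13, 14, 14, 14, 15 for n = 21 to 32. Acceptable rate 0.25; stated crossing probability 0.05.

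**Method.** Let f_n(k) be the probability of k counted stops among n patients with no crossing so far, and p the counted rate. Then f_n(k) = (1 − p)·f_{n−1}(k) + p·f_{n−1}(k − 1). At each n, the probability at k ≥ b_n is removed and added to the crossing probability.

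**The plan's own figure.** At p = 0.25 the result is 0.045. Each b_n is the smallest count whose binomial tail at 0.25 is at most 0.0156. The next looser level, 0.015625, gives 0.057. The stated 0.05 is therefore the ceiling of a discrete Pocock-type boundary, and the table is sound.

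**If every toxicity stop is counted.**

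| True rate | 0.25 | 0.30 | 0.35 | 0.40 | 0.50 |
|---|---|---|---|---|---|
| P(halt) | 0.045 | 0.124 | 0.267 | 0.463 | 0.831 |

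**If some are not counted.** Let T be the true toxicity-stop rate and u the proportion of all patients with an uncounted toxicity stop. The documents give neither T nor u; both are assumed. If uncounted patients stay in n, p = T − u. If they leave n because they lack three months of follow-up, p = (T − u)/(1 − u), with n still running to 32.

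| T | u (share of stops) | P(halt), all counted | Stay in n | Leave n |
|---|---|---|---|---|
| 0.40 | 0.05 (1 in 8) | 0.463 | p = 0.35: 0.267 | p = 0.35/0.95: 0.335 |
| 0.40 | 0.10 (1 in 4) | 0.463 | p = 0.30: 0.124 | p = 0.30/0.90: 0.212 |
| 0.50 | 0.10 (1 in 5) | 0.831 | p = 0.40: 0.463 | p = 0.40/0.90: 0.645 |

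**Rare named risks.** Section 1.3.3 gives lactic acidosis as 0.03 per 1000 patient-years and hepatotoxicity as below 0.1%. For 32 patients over one year the expected numbers are 32 × 0.00003 ≈ 0.001 and fewer than 32 × 0.001 = 0.032. Adding 0.1 percentage point to a counted rate of 25% (p = 0.251) moves the crossing probability only from 0.045 to 0.046.

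**Effect of a wider count.** If listed stops already run at 25% and newly counted stops add 5 points, p = 0.30 and the halt probability rises from 0.045 to 0.124. With 10 added points, p = 0.35 and it is 0.267.

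**The case against.** The best defence is that counting defined, graded events rather than voluntary stops is a reasonable choice in an open-label trial, and that the stated error rate is consistent if 25% is read as the rate of listed stops. Reason (2) already covers paired grade 2 events in any organ system, and reason (3) might absorb a woman who cannot tolerate 850 mg daily. The documents do not suggest 40–50% toxicity stops: section 1.3.3 puts gastrointestinal effects of any kind at about 30% of patients, and the window study in 1.3.2, though only 2–4 weeks long, reports two grade 1 toxicities and no discontinuation for them.

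Much of this stands. The size is conditional, and leaving patient-requested stops out is more defensible than leaving out investigator-made stops for related toxicity. What it does not answer is the gap between the purpose stated in 8.2 and 4.4 and the three-item count. Reason (3) is worded as a dose requirement, and the documents do not say whether it takes in other intolerance stops.

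A reader might infer that severe toxicity such as lactic acidosis could go unnoticed. The documents do not support that. Serious events are entered within 24 hours (7.3.2), unanticipated problems go to the IRB within 7 days (7.3.3), patients are called weekly for two weeks and then every 30 days (4.4), and the investigator monitors continuously with quarterly-to-annual committee review (7.4). Nor would counting one such event halt the trial, since the earliest boundary is 4 of 4.

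**Conclusion.** The point holds for the boundary alone. As written, b_n tracks listed stops, while 8.2 and 4.4 present it as tracking stops caused by toxicity, and the two differ whenever a related toxicity stop falls under another clause. The table and its error rate are correct for what is counted.

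The loss of sensitivity could be substantial, but its size rests on an assumed true rate, an assumed uncounted share, and a denominator rule that 8.2 leaves open for early stoppers. The fall from 46% to 12% or 21% is an illustration, not a forecast. The rare risks named in 5.1.6 do not drive it; more common related side effects that end in an unlisted stop would. The change is worth making because it brings the count into line with its stated purpose.

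**What to change.** Reconcile 8.2 with 4.4 and 4.7 so that b_n counts every discontinuation of metformin attributed to metformin-related toxicity, whichever clause it is recorded under. State explicitly whether a patient-requested stop for a related adverse event counts, and that patients who stop for toxicity before three months remain in n.

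The b_n table can stay, provided the sponsor confirms that 25% is the acceptable rate for the wider event. If it is not, the boundary has to be recalculated.

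The drafting cost is a sentence or two. Reasons for removal already go into the eCRF (4.9), and relationship to study drug is already recorded for adverse events (7.2). The operating cost is the higher chance of a pause for DSMC review shown in the working.

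The patient-level discontinuation criteria are a separate matter: the sponsor's clinical team should reconcile them with the risks named in 5.1.6. No criterion is proposed here.
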